### 4.3 General study outline

The total duration of the study is planned to be about 14 weeks for each subject, but it may be longer if required for scheduling purposes (e.g. availability of PET slots, subject's schedule). During the study, the subjects will have 5-6 study visits, depending on the need for safety visits (visit 2; see Table 3). Two of these visits, screening visit 2 and visit 2, may performed as a remote visit (i.e. telephone contact), if deemed sufficient by the investigator. In addition, unscheduled visits may occur at any time, if considered necessary for subject safety. The study includes a screening/run-in period (up to 6 weeks) and a treatment period (approximately 8 weeks). Both the screening/run-in and the treatment period may be longer, if necessary (see Section 7.1 for further details).

The subjects who sign the ICF will enter the screening/run-in period of the study. All study-related procedures will be performed only after the ICF has been signed. During the first study visit, the investigator will consider the subject's eligibility based on his/her medical history and current clinical status (including e.g. BP). If based on

these considerations, the subject is found to be likely to fulfill all of the inclusion criteria and none of the exclusion criteria, the subject will be switched to valsartan treatment and it will replace his/her previously used ACEI or ARB treatment during the screening/run-in period. The starting dose of valsartan will be 80 mg BID or if the dose of previous RAAS blockage medication has been higher, the valsartan dose will be 160 mg BID to ensure that the subjects' medication level is not down-titrated in the beginning of the screening/run-in period. Approximately one week after the screening visit 1, screening visit 2 will be scheduled in order to evaluate the safety and efficacy of the ongoing valsartan treatment. If deemed sufficient by the investigator, screening visit 2 can be performed remotely. If so, safety blood sampling, eligibility criteria review, adverse events and concomitant medication must be assessed. Only subjects who tolerate 80 mg BID or 160 mg BID of valsartan and can maintain a stable dose for at least 4 weeks will be eligible to enter into the treatment period.

After the screening evaluations and confirmation of eligibility, the subjects will be allocated randomization numbers and randomized to receive the treatment assigned to each number in a blinded manner. Study drugs will be dispensed by an unblinded member of the study team member during the treatment period while the study personnel directly involved in the clinical assessments will remain blinded throughout the study. The starting dose for each subject in the sacubitril/valsartan arm will be 100 mg BID and in the valsartan arm 80 mg BID or 160 mg BID (see Figures 2 and 3). The study subjects will return to the study center 2-3 times during the treatment period at the following time points: approximately 2 weeks (visit 1), 3 weeks (visit 2) and 8 weeks (visit 3) after the start of the treatment period.

During visit 1, treatment tolerability will be evaluated and possible dose up-titration will be considered. Every subject should be attempted to be up-titrated to the next dose level (sacubitril/valsartan 200 mg or valsartan 160 mg, if the latter needed), if clinically possible. If up-titration is not possible, the starting dose should be maintained. The intent of visit 2 (week 3) is to confirm subject safety on the dose level that is likely to be maintained for the rest of the study. If deemed sufficient by the investigator, visit 2 can be performed remotely. If so, safety blood sampling, adverse events and concomitant medication must be assessed.

After visit 2, if clinically indicated, the dose of the study treatment may be modified (up- or down-titrated) up to week 4. If study drug dose is modified within this time, an unscheduled visit should be performed to assess subject safety on the new dose level. During the treatment period, the subjects will self-administer two tablets from two study drug packages BID (one tablet from the study drug package containing the active treatment and one tablet from the study drug package containing the placebo). The last study visit will include the final efficacy assessments, i.e. the C-acetate PET-scan and the echocardiography.

The general study design is presented in Figure 1 and the study outline is presented in Table 3. The methods and timing of assessments and recording of efficacy, safety, tolerability and other measures are described in detail in Section 8.

Screening visit 2 and visit 2 are marked with (x) as they may be performed remotely, if deemed sufficient by the investigator. In addition, visit 2 may be omitted altogether, if no dose modification was made on the previous visit (visit 1).

### Table 3. General study outline

Study event	Screening visit 1	Screening visit 2 (R)	Baseline	Visit 1	Visit 2  (R)	Visit 3
	-5 weeks	- 4 weeks	day 1	day 14	day 21	week 8 
Informed consent	X					
Medical and surgical history	X					
Demographics	Х					
Physical examination 	X	X*	Х	Х	X*	X
Blood pressure and heart rate 	X	X*	Х	Х	X*	X
Safety blood samples 	X	X	X	X	X	X
Blood biomarker samples			Х			X
Decision on up- or down-titration				Х	X*	
Eligibility criteria review	X	X	Х			
Urine pregnancy test 			Х			X
 C-acetate PET-scan			X			х
Echocardio- graphy			Х			х
Randomization			Х			
Valsartan dispensing 	X	X*				
Study drug dispensing 			Х	Х	X*	
Instruction on drug intake 	Х	X*	X	X	X*	
Return of drug supplies 	2	X*	X	X	X*	х
Compliance check 		X*	X	Х	X*	Х
Adverse events			X			
Concomitant medications			Х	22 - 7		

R – If deemed sufficient by the investigator, screening visit 2 and visit 2 can be performed remotely (i.e. by telephone). If so, safety blood sampling, (eligibility criteria for screening visit 2 only), adverse events and concomitant medication must be assessed. If the visit is performed as a remote visit, assessments marked with "\*" do not need to be performed.

Visit 2 is a safety visit to be performed only for subjects whose dose was modified on visit 1 and/or if clinically indicated based on the investigator's decision. For subjects whose dose is not up-titrated on visit 1, visit 2 may be omitted.

 Visit 3 will be performed after the study treatment has been on a stable dose for a minimum of 6 weeks. It may be performed before or after 8 weeks, based on when the last dose modification was performed.

 Physical examination is part of clinical assessment and will take place on every site visit.

 Blood pressure and heart rate will be measured in a seated position, after at least 5 min of rest.

 Safety blood samples may be collected 1-2 business day(s) before the scheduled visit (with the exception of screening visit 1).

 For female subjects of childbearing potential.

 Study drugs will be dispensed by an unblinded member of the study team during the double-blinded treatment period. Valsartan may be dispensed by any member of the study team during the screening/run-in period.

 Instructions on drug intake have to be given at the start of each period and thereafter only if clinically indicated or significant non-compliance is detected.

 These study events include both the valsartan treatment during the screening/runin period and the double-blinded study drug treatment during the treatment period.

# 5 SUBJECTS

# 5.1 Source population

The subjects participating in this study will be patients with chronic HF, reduced EF and NYHA class II-III symptoms who fulfill all of the inclusion criteria and none of the exclusion criteria. The results of the screening evaluations will determine whether a subject can be included in the study or not.

# 5.2 Number of subjects

The planned number of enrolled study subjects is 60 (30 subjects/treatment arm). The aim is that at least 27 subjects/treatment arm finish the study according to the protocol. If discontinuations occur, the need of recruiting additional subjects to reach the targeted total number of subjects will be considered and carried out as appropriate. Thus, in case of discontinuations during the study, the number of enrolled study subjects may be larger than 60.

For justification of sample size, see Section 9.1.

### 5.3 Inclusion criteria

Subjects have to fulfill all of the following inclusion criteria to be eligible for inclusion in this study.

- 1. Voluntary, valid written informed consent (IC) obtained before any study-related assessment is performed.
- 2. Sufficient command of the Finnish or Swedish language to be able to fully understand the ICF and other study information and to be able to communicate with the study personnel.
- 3. Male and female subjects  $\geq$ 40 and  $\leq$ 80 years of age.
- 4. Documented chronic HF with left ventricle EF 25-35% and NYHA class II-III symptoms.
- 5. Systolic BP 110-160 mmHg at the time of randomization.
- 6. Optimal standard HF therapy according to ESC guidelines, including at a minimum beta-blockers in all subjects, at a stable dose for at least 4 weeks before the first screening visit.
- 7. Valsartan treatment tolerated at a dose of 80 mg or 160 mg BID for at least 4 weeks during the screening/run-in period.
- 5.4 Exclusion criteria

Subjects fulfilling any of the following exclusion criteria are not eligible for inclusion in this study.

- 1. Predicted poor compliance or inability to communicate well with the investigator or the study center personnel.
- 2. Current acute or subacute decompensated HF.
- 3. Presence of acute coronary syndrome, stroke, transient ischemic attack or other major cardiovascular event or cardiovascular procedure within 3 months before screening.
- 4. Coronary or carotid artery disease likely to require surgical or percutaneous intervention within the 6 months after randomization.
- 5. Evidence of clinically significant renal, hepatic, hematological, gastrointestinal, pulmonary, metabolic-endocrine, neurological, urogenital or psychiatric disease that may constitute a health risk for the subject and/or would interfere with the evaluation of the results, as judged by the investigator.
- 6. Symptomatic hypotension that persists even after modification of concomitant medication(s), at any time during the screening/run-in period.
- Estimated glomerular filtration rate (eGFR) < 45 ml/min at any time during the screening/run-in period that persists even after modification of concomitant medication(s).
- 8. Serum potassium >5.2 mmol/l at any time during the screening/run-in period that persists even after modification of concomitant medication(s).
- 9. Serum creatinine > 1.5 x ULN (upper limit of normal) at any time during the screening/run-in period that persists even after modification of concomitant medication(s).

- 10. Contraindication to neprilysin inhibitor or ARB (such as previous angioedema or known intolerance).
- 11. Susceptibility to severe allergic reactions or known hypersensitivity to the active substances or to any of the excipients.
- 12. Intake of any medication that could affect the outcome of the study, interfere with the evaluation of the results or constitute a health risk for the study subject, as judged by the investigator.
- 13. Positive serology to human immunodeficiency virus antibodies (HIVAgAb), hepatitis C virus antibodies (HCVAb) or hepatitis B surface antigen (HBsAg) in medical history.
- 14. Unwillingness to use adequate methods of contraception while participating in the study and for 3 months after the last administration of the PET tracer.
- 15. Participation in another clinical drug study within 3 months prior to the first study treatment administration of this study.
- 16. Prior participation in an investigational PET study or other medical or occupational exposure to significant doses of ionizing radiation, as judged by the investigator.
- 5.5 Recruitment

The subjects will be recruited from the patient population of the hospital district of Southwest Finland. A description of the possible means of subject recruitment is included in the submission to the Ethics Committee (EC). The recruitment of subjects will start after approvals have been received from the EC and Competent Authority (CA).

The investigator or an appropriate designee will look over the medical records of the patients treated in the hospital district of Southwest Finland. If needed, colleagues of the investigator may be informed about the study to aid in recruitment. Possibly suitable subjects will be contacted and the person responsible for subject recruitment will first shortly brief the potential subjects about the study in layman's language. This first study-related contact may be performed also in person, if the subject candidate is on site. The main inclusion and exclusion criteria will be checked during telephone contact or face-to-face conversation. If an inclusion criterion is not fulfilled, or an exclusion criterion is fulfilled, this is immediately told to the subject, and the interview is terminated. If, according to this preliminary evaluation, the subject candidate might be eligible for the study, the procedures for providing the written subject information are discussed. The subject information leaflet and the ICF are handed over to the subject or delivered to him by post, e-mail or another method. The next steps in the recruitment process will be agreed upon, as convenient to the subject and as defined in the protocol. Upon the subject candidate's wish, a screening visit may be booked or performed on-site after signing the ICF (all study-related assessments will be performed after signing the ICF).

The subjects will be told what personal information of them will be collected and how it will be stored and processed. The collection of personal information is described in a Description of the Personal Data Register, which is kept in the Investigator's Study File (ISF) and is made available to the subjects, if they wish.

### 5.6 Study subject screening log and identification log

The investigator will keep a subject identification list in the ISF. The list includes information to link all study-related records to a subject, i.e. randomization list, case report forms (CRFs) and source data. Furthermore, a subject screening log of all subjects screened for the study will be maintained. The identity of the subject (screening number, the subject's first name, last name and personal identity number), date of IC, date of entry or date of exclusion and the reason for exclusion, if applicable, for those recruited for screening but not fulfilling the criteria and therefore excluded, should be recorded on the list.

# 5.7 Instructions concerning lifestyle and concomitant treatments

The subjects are instructed to keep their usual dietary and exercise habits during their participation in the study. Blood donation is not allowed during the study. Female subjects of childbearing potential and male subjects with female partners of childbearing potential should be instructed to use adequate methods of contraception while participating in the study and for 3 months after the last administration of the PET tracer. Urine pregnancy tests will be performed for females of childbearing potential prior to each PET scan. Use of alcohol and caffeine-containing beverages is forbidden for 12 h before each PET-scan. In addition, a study subject shall not participate concurrently or have participated in any other clinical drug trial within 3 months prior to entry into this study. Instructions regarding concomitant treatments can be found in Section 6.5.

# 5.8 Withdrawal of subjects

Study subjects are free to withdraw from the study at any time without providing a reason. However, the investigator should try to find out the reason and document it on the corresponding CRF page. A subject may also be withdrawn from the study if his/her adherence to the study protocol is not acceptable. A study subject needs to discontinue the study if the investigator considers that continuation in the study would be detrimental to the subjects well-being. The following situations should result in the withdrawal of the subject, unless the investigator considers it safe for the subject to continue in the study, possibly after dose modifications of the study drug or other concomitant medication:

- persistent symptomatic hypotension after randomization;
- serum potassium > 5.2 mmol/l after randomization;
- serum creatinine > 1.5 x ULN after randomization.

If the subject continues in the study, the investigator has to document his/her decision in the source documents and verify continuous subject safety with e.g. repeat BP surveillance and/or laboratory safety measurements during unscheduled visit(s).

Irrespective of the reason for discontinuation, discontinued study subjects should be invited for an unscheduled visit as soon as possible in order to perform final safety assessments (incl. BP, safety laboratory tests and possibly other tests judged necessary by the investigator). The CRFs should be as complete as possible.

If discontinuations occur, the need of recruiting additional subjects to reach the targeted total number of subjects will be considered and carried out as appropriate. Discontinued study subjects are not allowed to re-enter the study.

### 5.9 Information to be collected on screening failures

From subjects screened but not included in the study, the following data will be collected on CRFs: date of IC, demography (year of birth, sex and race), the inclusion/exclusion criterion/criteria causing the exclusion and the date of the decision of exclusion.

### 6 TREATMENTS

### 6.1 Investigational treatment sacubitril/valsartan

The IMP, sacubitril/valsartan, will be provided in appropriately labelled study drug packages of the different strengths of the active drug. Also, corresponding placebo tablets that are similar in appearance to the active sacubitril/valsartan will be provided. The following strengths of sacubitril/valsartan will be available:

- sacubitril/valsartan 100 mg: containing 49 mg sacubitril/51 mg valsartan,
- sacubitril/valsartan 200 mg: containing 97 mg sacubitril/103 mg valsartan.

The IMP is manufactured by Novartis in accordance with GMP guidelines. The labelling will be also done in compliance with GMP regulations after which the study drug will be released at Novartis. The sacubitril/valsartan will be stored in the Heart Center in locked cabinets according to the instructions provided in the SPC. The subjects will receive their study treatment according to the randomization list which contains randomization numbers and allocated treatments. The study drugs will be dispensed by an unblinded member of the study team and the subjects will take the study drugs and corresponding matching placebo tablets at home BID. After the randomization, 50% of the subjects will start in the sacubitril/valsartan treatment arm on a starting dose of 100 mg BID (see Figure 2). There is one visit scheduled for possible up-titration of the dose (visit 1) and during this visit every subject should be attempted to be up-titrated to the next dose level (sacubitril/valsartan 200 mg or valsartan 160 mg), if clinically possible and if the latter needed. If up-titration is not clinically possible, the starting dose should be maintained. During the treatment period, subjects will receive new study drug packages (active drug and placebo) from the unblinded drug dispenser, as applicable.

The study subjects and all investigators and other study personnel participating in the assessments will be kept blinded to the treatments but not the dose level.

A schematic figure about the possible treatments and doses is shown in Figures 2 and 3.

Protocol CLCZ696BFI03

36(70)

Figure 2. Study treatment during the double-blind treatment period with sacubitril/valsartan.

Protocol CLCZ696BFI03

37(70)

Figure 3. Study treatment during the double-blind treatment period with valsartan.

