# 4 STUDY DESIGN

# 4.1 Type and design of the study

This is a phase IV, prospective, randomized, double-blind, double-dummy, parallelgroup study performed at a single center that is formed by

. The subjects enrolled into this study will be patients with chronic HF who fulfill all of the inclusion criteria and none of the exclusion criteria. No more than 50% of the study subjects are allowed to have diabetes. The study will have two treatment arms, the sacubitril/valsartan treatment arm and the valsartan treatment arm, and the subjects will be randomized into these arms in a 1:1 ratio. The study will be performed in a double-blind manner in regards to the treatment the subjects receive during the treatment period. As the sacubitril/valsartan and valsartan tablets are not similar in appearance, the study will be performed in a double-dummy manner in order to maintain blinding, i.e. the subjects will take 2 tablets BID, either active valsartan + placebo for sacubitril/valsartan or active sacubitril/valsartan + placebo for valsartan. Regardless of the treatment arm a subject is in, the study drug will be up-titrated to the highest tolerated dose level during the scheduled study visits. The different strengths of the two study drugs are not identical in appearance so the possible dose modification(s) during the treatment period cannot be performed in a blinded manner. Subjects will start on valsartan 80 mg BID or sacubitril/valsartan 100 mg BID dose and there will be only one scheduled up-titration visit after the randomization. Exception for this are the subjects that are on valsartan 160 mg BID dose during the run-in phase. These subjects will be randomized directly to valsartan 160 mg BID or sacubitril/valsartan 100 mg BID. Subjects that are randomized to valsartan arm will have similar visit after which they will continue on the same dose. For subjects that were randomized from valsartan 160 mg BID to sacubitril/valsartan 100 mg BID the dose will be up-titrated to 200 mg BID if clinically possible. If clinically indicated, dose alterations will be allowed up to week 4 after randomization. In order to be eligible for the final study assessments on visit 3 (i.e. the C-acetate PET-scan and echocardiography), the subjects have to be on a stable dose for at least 6 weeks on one of the following treatment options: valsartan 80 mg BID or 160 mg BID or sacubitril/valsartan 100 mg BID or 200 mg BID. Study drug dispensing during the treatment period will be performed by an unblinded member of the study team and the study drugs will be self-administered by the subjects at home. To achieve similar groups, the number of subjects with renal insufficiency (GFR 45-60 or >60 mL/min/1.73m^2) and/or diabetes mellitus (on insulin or oral glucose-lowering therapy) will be balanced in the treatment arms by stratified randomisation. The baseline HF therapy (the number of subjects that are on valsartan 160 mg BID at the time of randomization) will be also balanced between the treatment arms.

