
### 4.2 Randomization and blinding

The subjects will be randomized in a 1:1 ratio to one of the two treatment arms, either the sacubitril/valsartan treatment arm or the valsartan treatment arm. Stratified randomization will be used to achieve similar groups in terms of patients with renal insufficiency (GFR 45-60 or >60 mL/min/1.73m^2) and/or diabetes mellitus (on insulin or oral glucose-lowering therapy, no more than 50 % of patients in the study are allowed to be diabetic). The baseline HF therapy (the number of subjects that are on valsartan 160 mg BID at the time of randomization) will also be taken into account during randomization.

Study drug packages will be provided from Novartis with removable labels stating the treatment. Treatment allocation will be done by an un-blinded member of the study team who will remove the labels stating the treatment before distributing the study drug packages to the subjects.

The randomization will be generated by an independent statistician at using SAS®.

Sealed envelopes containing the individual treatment codes (randomization number and the corresponding treatment) will be stored adjacent to the investigational medicinal products (IMPs) until the end of the trial. In case of an emergency requiring immediate knowledge of the treatment administered, the code of an individual subject may be opened. The reasons for opening the code have to be documented and the subject has to be discontinued from the study. The study monitor and the sponsor should be immediately informed about breaking of the treatment code.

This study will be conducted in a double-blinded fashion regarding the treatment (i.e. sacubitril/valsartan or valsartan). As the sacubitril/valsartan and valsartan tablets differ in appearance, the study has to be performed in a double-dummy manner with the subjects taking one active tablet and one placebo tablet BID. The different

strengths of the two study drugs are not identical in appearance so the possible dose modification(s) during the treatment period cannot be performed in a blinded manner. However, the up-titration step will be aligned in both treatment arms – the subjects will start on valsartan (80 mg BID or 160 mg BID) or sacubitril/valsartan (100 mg BID) and there will be only one scheduled up-titration visit after the randomization. The subjects that start from valsartan 160 mg BID will have similar scheduled visit but will stay on the same dose.

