### 6.2 Control treatment

Valsartan will be used as control treatment during the study. Its use aims to standardize background therapy for efficacy and hemodynamic effects in order to assess the incremental effects of combined angiotensin receptor (ATR) inhibition and neprilysin inhibition therapy as compared to ATR inhibition alone. Valsartan will replace previously used ACEI or ARB in all subjects during the screening/run-in period on a dose of 80 mg BID or 160 mg BID, if the dose of previous RAAS blockade was higher than 80 mg BID or equivalent. In order to be eligible for the study, a minimum dose of valsartan 80 mg BID has to be tolerated by the subject.

Valsartan will be provided in appropriately labelled study drug packages of the different strengths of the active drug. Also, corresponding placebo tablets that are similar in appearance to the active valsartan will be provided. The following strengths of valsartan will be available:

- valsartan 80 mg (used in both the screening/run-in period not blinded and also after randomization in a blinded manner),
- valsartan 160 mg (used in both the screening/run-in period not blinded and also after randomization in a blinded manner).

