During the screening/run-in period, the subjects will receive valsartan treatment that will replace their previous ACEI or ARB HF therapy. Valsartan during the screening/run-in period may be dispensed by any member of the study team. The screening/run-in dose of valsartan (80 mg BID or 160 mg BID) will be decided by the investigator based on the subject's clinical status, prior HF therapy and concomitant medications. The subjects will have a scheduled safety and efficacy assessment visit during the screening/run-in period (screening visit 2 in the study schedule, Table 3). If deemed sufficient by the investigator, screening visit 2 can be performed remotely. If so, safety blood sampling, eligibility criteria review, adverse events and concomitant medication must be assessed.

Dose reduction of a loop diuretic is allowed during the screening/run-in to prevent hypotension. Unscheduled visits may be performed at any time during the screening/run-in period. Study visit should be performed as close proximity to the stated day in the study schedule (Table 3) as possible.

The subject has to tolerate at the minimum 80 mg BID valsartan at a stable dose for minimum of 4 weeks in order to be eligible for the treatment period. Before the PET-scan, a urine pregnancy test should be performed for female subjects of childbearing potential. During the baseline visit, PET-scan and echocardiography will be done and blood samples for biomarker assessment will be drawn. After all other study procedures are performed at the baseline visit and the subject is deemed eligible for the study, he/she will be randomized and start the double-blinded treatment period.

The results for the laboratory tests taken during the on-site screening visits do not need to be available before decision-making (i.e. starting valsartan treatment), but they have to be reviewed as soon as possible after they become available in order to ensure subject safety. All screening/run-in period laboratory results must be available and reviewed before randomization, except the results of the laboratory tests taken on the baseline visit, as randomization is performed on the same day as the baseline visit.

Adverse events and changes in concomitant medications will be recorded throughout the screening/run-in period.

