highest tolerated dose, up to 160 mg BID (if needed) for valsartan and up to 200 mg BID for sacubitril/valsartan. There will be one visit scheduled for possible up-titration of the dose (visit 1) and during this visit every subject should be attempted to be uptitrated to the next dose level (sacubitril/valsartan 200 mg or valsartan 160 mg, if needed), if clinically possible. If up-titration is not clinically possible, the starting dose should be maintained. At the minimum, 80 mg BID of valsartan or 100 mg BID of sacubitril/valsartan has to be tolerated by the subject in order to finish the study - if these doses are not tolerated, the subject has to be withdrawn from the study. The decision to up-titrate the dose will be done by the investigator during the study visits based on the subject's clinical status and the safety assessments, incl. BP and safety laboratory tests. The laboratory results, if taken on the days of the on-site visits, do not need to be available before decision-making but they have to be reviewed as soon as possible to ensure subject safety. If the safety blood samples are collected 1-2 business day(s) before the scheduled visit, the laboratory results have to be available and reviewed before decision-making. Dose reduction of a loop diuretic is allowed during the up-titration to prevent hypotension.

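### In subjects entering on valsartan 160 mg BID, the open run-in dose plus an unmasked dose level identifies the arm, so the stated blinding of assessors is not secured in that stratum

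*Protocol*

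**What the plan says.** **Masking.** Protocol 4.3 states that "study personnel directly involved in the clinical assessments will remain blinded throughout the study", and SAP 1.1 repeats it. Protocol 6.1 is narrower: "study subjects and all investigators and other study personnel participating in the assessments will be kept blinded to the treatments but not the dose level". Protocol 4.1 and 4.2 accept that dose changes cannot be made blind, because the tablet strengths look different.

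**Run-in.** Protocol 7.1 says "The screening/run-in dose of valsartan (80 mg BID or 160 mg BID) will be decided by the investigator". Protocol 6.2 makes the run-in open, listing "valsartan 160 mg (used in both the screening/run-in period not blinded and also after randomization in a blinded manner".

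**Start of treatment.** For subjects on 160 mg BID at run-in, Protocol 4.1 says: "These subjects will be randomized directly to valsartan 160 mg BID or sacubitril/valsartan 100 mg BID". Under the synopsis (comparative drug), subjects on 80 mg BID at run-in start on valsartan 80 mg BID or sacubitril/valsartan 100 mg BID.

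**Visit 1.** Protocol 4.2 says "the up-titration step will be aligned in both treatment arms", but then adds: "The subjects that start from valsartan 160 mg BID will have similar scheduled visit but will stay on the same dose". Under Protocol 4.1, subjects who moved from 160 mg BID to sacubitril/valsartan 100 mg BID go up to 200 mg BID at that point if clinically possible. Protocol 7.2 says: "The decision to up-titrate the dose will be done by the investigator during the study visits".

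**Endpoint.** SAP 2.4.1 builds cardiac efficiency from systolic pressure, stroke volume, heart rate, LV mass and the PET clearance rate. Protocol 8.2.2 and 8.3.2 leave imaging procedure, and pressure and heart rate monitoring during imaging, to separate written instructions.

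**The concern.** The double-dummy hides which tablet is active. It does not hide a dose level that Protocol 6.1 expressly leaves open. In the 160 mg stratum the two arms start at different levels, so dose level stands in for treatment there. No visible text acknowledges this.

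What is at stake is a masked reading of visit 3. Stroke volume and LV mass come from echocardiography, and Protocol 8.2.2 allows cardiac output from either outflow-tract Doppler or LV volumes. At least one measurement choice is therefore open in the protocol, although the imaging instructions may settle it. Following Protocol 6.1 as written would let personnel who take part in the assessments know the dose level. With the run-in dose as well, they would know the arm.

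**Working it through.** **1. Which arms fit each combination.** Read dose level as a step. The lower step is valsartan 80 mg or sacubitril/valsartan 100 mg; the upper step is valsartan 160 mg or sacubitril/valsartan 200 mg. This pairing follows the valsartan equivalences in Protocol 2.3. It is the more lenient reading, since the dose in milligrams would name the drug in either stratum.

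| Run-in valsartan | Starting level | Arms that fit | Chance of naming the arm (1:1) |
|---|---|---|---|
| 80 mg BID | lower | both | 0.5 |
| 80 mg BID | upper | none | – |
| 160 mg BID | lower | sacubitril/valsartan only | 1.0 |
| 160 mg BID | upper | valsartan only | 1.0 |

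**2. Who can hold both facts.** The investigator sets the run-in dose (Protocol 7.1), decides on up-titration (7.2) and is unmasked to dose level (6.1). Subjects took the run-in tablets openly and are also unmasked to dose level. For image analysts the documents available do not settle the matter.

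**3. What visit 1 adds.** In this stratum the valsartan arm starts at its top level, while the sacubitril/valsartan arm has one step left. The visit is aligned; the planned dose step is not. A step up therefore points strongly to sacubitril/valsartan, but not with certainty. The synopsis allows one dose modification outside scheduled visits, and Protocol 7.2 allows changes in the first 4 weeks. A valsartan subject reduced before visit 1 could thus be raised again. The absence of a step settles nothing, because sacubitril/valsartan may be held at 100 mg BID.

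**4. Size.** Inputs from Protocol 9.1 and SAP 3: CV of efficiency 19.7%, target change 15%, 27 per arm, α = 0.05, β = 0.2. Taking 19.7 as the SD of change in percentage points:

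- Plan's figure: n per arm = 2 × [19.7 × (1.960 + 0.842) / 15]² = 27.08, against the stated 27. The SD is thus used as the plan appears to use it.
- SE of the overall difference = 19.7 × √(2/27) = 5.36 points.

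The share of subjects on 160 mg BID is not given, so 20%, 30% and 50% are assumptions, with equal arms inside the stratum. A 1-point between-arm reading differential confined to the stratum moves the overall difference by the share:

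| Assumed share | Shift, points | Shift / 5.36 | Shift / 15 | n per arm in stratum (27 × share) | Stratum SE, 19.7 × √(2/n) |
|---|---|---|---|---|---|
| 20% | 0.2 | 0.04 | 1.3% | 5.4 | 12.0 |
| 30% | 0.3 | 0.06 | 2.0% | 8.1 | 9.8 |
| 50% | 0.5 | 0.09 | 3.3% | 13.5 | 7.6 |

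The last two columns describe a plain comparison of arms within the 160 mg stratum, where the differential would count in full.

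**The case against.** The strongest reply is that the harmful step is not shown. The primary endpoint comes from imaging, and bias needs a reader who holds both the run-in dose and the dose level. The separate imaging instructions may already prevent that. The documents do not say whether a titrating investigator also analyses images, and baseline imaging precedes randomisation. This stands. It limits the point to masking that is asserted but not secured.

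A second reply is that Figures 2 and 3, not shown here, may pair dummy strengths so that tablets look alike in both arms. That could protect against recognition by appearance. It would not remove the statement in Protocol 6.1 that dose level is not masked.

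A third is that the 1-point differential is arbitrary and its effect on the overall estimate small. Both are true. The calculation gives scale only and predicts neither the size nor the direction of any differential.

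A reader might also infer that a visit 1 up-titration proves the arm. The permitted earlier dose changes rule that out as a certainty. A reader might further infer that the exploratory within-stratum estimates in SAP 2.4.6 would carry any differential undiluted. That holds only if the interaction model uses run-in dose alone. Randomisation also uses renal function and diabetes, and SAP 2.4.6 does not say how the strata enter. Only the descriptive split of the primary endpoint in SAP 4 is clearly by run-in dose.

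**Conclusion.** The point holds for one stratum. In subjects entering on valsartan 160 mg BID, run-in dose and starting level together identify the arm, and Protocol 6.1 leaves subjects, investigators and personnel taking part in assessments unmasked to dose level. The unqualified assurance in Protocol 4.3 and SAP 1.1 is therefore not secured there, and no visible text repairs it.

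A reader might conclude that the trial as a whole is unblinded, or that its primary result is biased. The documents support neither. The starting level is uninformative in the 80 mg stratum, reader access to the two facts is not documented, and the overall shift is 0.04 to 0.09 SE per point of differential at the assumed shares. Those figures rest on the assumed share, equal arms within the stratum and 19.7% used as the SD of change. The matter should still be corrected, because the gap follows from the protocol's own wording and closing it is cheap.

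**What to change.** Leave doses, titration rules and kits as they are.

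1. **Protocol 6.1.** Keep the sentence on blinding to treatment. Limit knowledge of dose level to subjects, the unblinded dispenser and the investigators who manage titration. Add: *Visit 3 PET and echocardiography are analysed from coded images by existing staff who have no access to run-in dose, dose level or titration history.* Put the same rule in the imaging instructions cited in Protocol 8.2.2 and 8.3.2. Where existing staffing allows, withhold this information also from staff who acquire images and measure blood pressure and heart rate during imaging, since both measurements enter the endpoint.
2. **Protocol 4.2, 4.3 and 6.1, and SAP 1.1.** Reconcile them. State that the up-titration visit is aligned in all subjects but the dose step is not in the 160 mg stratum, and that full masking in that stratum applies to the image analysts, not to the titrating investigators.

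The cost is wording in these sections and the imaging instructions, coding of visit 3 images, and some separation of information between titrating and imaging staff at a single centre. Another reader would be needed only if a titrating investigator also analyses the images, which the documents do not say.
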